DLQI	Dermatology Life Quality Index
DCC	Data Coordinating Center
DSMB	Data Safety Monitoring Board
EI	Epidermolytic ichthyosis
ECG	Electrocardiogram
FDA	Food and Drug Administration
FIRST	Foundation for Ichthyosis and Related Skin Types
HIV	Human Immunodeficiency Virus
IASI	Ichthyosis Area Severity Index
IASI-E	Erythema subscore of Ichthyosis Area Severity Index
IASI-S	Scaling subscore of Ichthyosis Area Severity Index
IP	Investigational Product
IRB	Institutional Review Board
ITT	Intention-to-treat
IQoL-32	Ichthyosis Quality of Life- 32 items
LI	Lamellar ichthyosis
LOCF	Last-Observation Carried Forward
m-CISI	Modified congenital ichthyosis severity index
mITT	modified Intention-To-Treat
MMRM	Mixed-effect Model Repeated Measures
NRS	Numerical Rating Scale
NS	Netherton syndrome
PASI	Psoriasis Area Severity Index
SAE	Serious Adverse Event
s.c.	Subcutaneous
TEWL	Transepidermal water loss

Product: Secukinumab

Protocol Number: CAIN457AUS05T

Date: 14 July 2018

7

PROTOCOL SYNOPSIS

Title: A Pilot Study to Evaluate the Efficacy and Safety of Secukinumab in the Treatment of Patients with Ichthyoses

Sub-Study: A Multicenter Study with a Randomized, Double-Blind, Placebo-Controlled Period, Followed by an Open-Label Maintenance Dosing Period to Evaluate the Efficacy and Safety of Secukinumab in Patients with Ichthyoses

Investigation Type: Drug

Study Type: Randomized Control Trial

Purpose and Rationale: The ichthyoses are a group of lifelong genetic disorders which share characteristics of generalized skin thickening, scaling and underlying cutaneous inflammation. The vast majority are orphan disorders and are associated with extremely poor quality of life related to social ostracism from altered appearance, associated itchiness and discomfort, and functional limitations from the skin disease. Among the most common of these orphan disorders are autosomal recessive congenital ichthyosis (ARCI), Netherton syndrome (NS) and epidermolytic ichthyosis (EI). Therapy is time-consuming for patients or parents and is supportive, focusing on clearance of the scaling. There are no therapies based on our growing understanding of what causes the disease. We have recently found marked elevations in interleukin-17A (IL-17A) and IL-17-related cytokines in the skin of individuals with ichthyosis, likely explaining their inflammation. Psoriasis, another inflammatory skin disorder with redness and scaling, has now been shown to result from IL-17 pathway activation and IL-17A inhibition is the most effective therapy known to treat psoriasis. We propose that IL-17-targeting therapeutics will safely suppress the inflammation and possibly the other features of ichthyosis, improving quality of life. We propose to treat adults with ARCI and at least moderate erythema with subcutaneously administered anti-IL-17 antibody (secukinumab) and to serially assess clinical response to this therapy and its safety.

Primary objective: To evaluate the efficacy and safety of secukinumab in the treatment of ichthyosis (as determined by reduction in Ichthyosis Area Severity Index (IASI) at week 16, and by monitoring for the occurrence of bacterial/fungal mucocutaneous infection at week 16)

Secondary objectives:

1. To evaluate reduction in other skin severity assessments
2. To evaluate improvement in quality of life assessments
3. To evaluate the reduction in skin and blood IL-17A expression as a function of clinical response.
4. To determine response biomarkers to secukinumab in treated patients.
5. To define the cellular and molecular immune profiles of patients with ichthyoses.

Product: Secukinumab

Protocol Number: CAIN457AUS05T

Date: 14 July 2018

8

These clinical indices will be assessed as per the Schedule of Assessments flowchart (Appendix 1) and require minimal input or time commitment from the study participants, but are critical to analyze trends with time.

Safety Objectives: Assess the short term (16 weeks) and long term (32 and 52 weeks) safety profile of secukinumab 300 mg s.c. in subjects with ARCI, NS and EI by monitoring for adverse events and deleterious alterations in clinical examination or clinical laboratory results.

Study Design: After the screening period (21-28 days), the study begins with a double blind trial of placebo compared to secukinumab. Subjects will be stratified by disease subtype (ARCI-CIE, ARCI-LI, EI and NS) in blocks of 4 and randomized in a 1:1 ratio of one subject treated with secukinumab to one subject treated with placebo for 15 weeks as follows: Each subject will receive secukinumab or placebo at Baseline (Day 0), weeks 1, 2, 3, 4, and every 4 weeks thereafter (week 8, week 12) until 15 weeks have elapsed. At week 16 all subjects will receive 300mg secukinumab. At week 17, 18, and 19 subjects will receive either secukinumab (if previously on Placebo) or Placebo (if on secukinumab originally), followed by open-label secukinumab 300mg every 4 weeks starting on week 20 up to week 48. The final assessment will be the end of study visit (week 52).

Visit Number	1	2	3	4	5	6	7	8	9	10	11	12
						COW1*	OLW1**	OLW4**	OLW12**	OLW20**	OLW28**	OLW32**
	Screen (28 d-21 d of Day 0)	Baseline/ Day 0	Wk 4	Wk 8	Wk 12	Wk 16	Wk 20	Wk 24	Wk 32	Wk 40	Wk 48	Wk 52
Drug supplied	0	4 doses Due on week 0, 1,2,and 3	1	1	1	4***	1	2	2	2	1	6

*Crossover Week (COW): Crossover Week 1 dosing occurs in study visit. COW2-4 dosing occurs at subject home weekly.

**Open Label Week (OLW): Open label Weeks 1, 4, 12, 20, and 28 occurs in study visits. OLW8, 16, and 24 dosing occurs at subject home every 4 weeks.

*** Because dose on week 16 is 300mg secukinumab and no placebo will be given for any patient on that week, two prescriptions must be written to differentiate the crossover dose on week 17, 18, and 19.

Multi-Center: Yes

Number of Centers: 2

Blinding: Observer-Blind Yes
 Subject-Blind Yes
 Double-Blind Yes

Study Duration: The clinical portion of the study will include 1.5 years for patient recruitment and up to 52 weeks of treatment, bringing the total maximum clinical study duration to 2.5 years.

Product: Secukinumab

Protocol Number: CAIN457AUS05T

Date: 14 July 2018

9

Test Medication: Secukinumab 300 mg s.c. (Cosentyx®)

Control Medication: Placebo s.c. (supplied by Novartis)

Study Population: 40 evaluable subjects

Subjects must be at least 18 years of age with a diagnosis of ARCI, EI or NS and must show at least moderate erythema. These subjects will primarily come from the east coast (around New York City) and Midwest (around Chicago), but will be open to any subjects who are able to comply with study requirements and meet criteria.

Inclusion Criteria

- Subject has provided informed consent
- Subjects are at least 18 years of age or older at the time of screening.
- Female subjects must not be pregnant or breast-feeding. Female subjects of child-bearing potential with a negative urine pregnancy test and using at least one form of contraception (abstinence allowed).
- Subjects must have a confirmed diagnosis of ARCI-LI, ARCI-CIE, EI or NS (either genotype or willingness to be genotyped)
- Subjects must be clinically judged to be immunocompetent.
- Subjects will have no allergy to secukinumab, latex, or components of the product..
- Subjects will have baseline laboratory testing (normal or non-significant CMP, CBC, HIV negative, hepatitis B, C negative, QuantiFERON®-TB gold negative).
- Subjects must have an erythema score of at least 18 on IASI and an IASI-E score of 12 (at least moderate severity of erythema) at baseline

Exclusion criteria

- Subjects who are unable to give informed consent or assent.
- Subjects without a confirmed diagnosis of ARCI, EI, or NS.
- Subjects who have a known allergy to secukinumab or to latex.
- Female subjects who are pregnant or who are considering becoming pregnant.
- Subjects who have prior biologic use targeting IL-17A/IL-17 receptor A or IL-12/IL-23 or who have prior use of TNF-alpha blockers.
- Subjects who have used a systemic retinoid or systemic anti-ichthyosis agent within 4 weeks prior to initiation.
- Subjects who have used topical retinoids or keratolytics within one week prior to initiation.
- Subjects who have used emollient on the area to be biopsied in the previous 24 hours
- Subjects who have a history or diagnosis of inflammatory bowel disease
- Subjects who are on any systemic immunosuppressive agent (i.e. cyclosporine)

Duration of Treatment: 40 ichthyosis-affected adults will be studied up to 52 weeks. The study will include an initial 16 weeks 1:1 placebo: secukinumab double-blind, randomized control phase, followed by a 4 week crossover period and 32 weeks open-label phase to assure long-term safety.

Product: Secukinumab

Protocol Number: CAIN457AUS05T

Date: 14 July 2018

Each subject will receive secukinumab or placebo at Baseline (Day 0), Weeks 1, 2, 3, 4, and every 4 weeks on week 8 and week 12. Then at Week 16 all subjects will receive 300mg secukinumab. For Weeks 17, 18, and 19, subjects if on secukinumab originally will receive 3 weekly injections of placebo. For Weeks 17, 18, and 19 subjects if previously on placebo will receive 3 weekly injections of secukinumab. During the Open label, they will continue to receive injections every 4 weeks for 32 additional weeks (up to week 48) with 4 weeks followup.

Treatment randomization scheme:

Week 0 -15	Week 16	Week 17, 18, 19	Week 20 – 48 (OLW1-28)
Randomized according to table; blinded	Open label	Crossover; blinded	Open label
A	A	B	A
B	A	A	A

*A=secukinumab B=placebo

Efficacy Assessments

- IASI: Ichthyosis Area Severity Index and subscores (IASI-E, IASI-S)
- CISI: Congenital Ichthyosis Severity Index
- A modified CISI (m-CISI), a new global assessment tool (for validation but not secondary endpoint assessment)
- Bodemer Ichthyosis Score (clinical burden of disease)
- Yale Ichthyosis Severity Index
- DLQI: Dermatology Life Quality Index
- iQoL-32: Ichthyosis-specific Quality of Life, including emotional impact
- 5-D Pruritus Scale
- Itch NRS: Numerical Rating System for pruritus
- TEWL (transepidermal water loss): Functional assessment of barrier

Note the severity assessments will be performed in tandem but blindly and without conferring by two physicians (IASI, CISI, m-CISI, Bodemer, Yale) and the CISI and m-CISI as well by the subject, allowing inter-rater reliability assessment. By doing this assessment at screening and 3-4 weeks later at baseline for those subjects who have no significant change in intervention, we will be able as well to evaluate intra-rater (test-retest) reliability.

Safety Assessments

- Adverse events and serious adverse events monitoring: adverse events of special interest include infections, particularly occurrence of bacterial or fungal mucocutaneous infection
- Laboratory assessments (e.g., hematology, clinical chemistry, urine pregnancy)
- Vital signs, physical examination

Other Assessments

- Photography

Product: Secukinumab

Protocol Number: CAIN457AUS05T

Date: 14 July 2018

11

- Skin biopsy (4.5 mm) for immunohistochemistry and mRNA expression (qRT-PCR) of 4 genes (IL-17A and three IL-17A induced genes for interpretation)
- Serum samples for cytokine analysis
- Skin swabs and scrapings to evaluate skin microbiome
- Tape strips to evaluate skin proteomics and lipidomics

Data Analysis

Statistical analysis of all clinical and translational studies will be performed by a statistician at the Icahn School of Medicine at Mount Sinai and .

The data from both centers that participate in this study will be combined for analyses. The primary analysis population will be based on a modified intention-to-treat (mITT) population, which is defined as all randomized patients who received at least one dose of the randomized treatment. Because the loading dose is given at baseline, this should effectively include all the randomized patients.

Efficacy and other data will be summarized. Descriptive statistics of demographics and other baseline characteristics will be presented for all subjects. For more details, refer to Section 9.2. The primary efficacy variable is the IASI (composite) at Week 16. The primary safety variable is the occurrence of bacterial and fungal mucocutaneous infections by Week 16. Differences in change over time between treatment and placebo will be assessed using a mixed-effect model repeated measures. Outcomes for weeks 0 to 16 for all the subjects from phase 1 and the outcomes for weeks 16 to 52 for subjects randomized with secukinumab in both phases will be considered. For more details, refer to Section 9. Safety will be evaluated by tabulations of adverse events and will be presented with descriptive statistics at each visit for each treatment group. The statistical evaluations will be organized by Treatment Phase (Weeks 0-16 and 16-48), and Post-Treatment Phase (weeks 48-52), as appropriate. AEs will be coded using the CTCAE, Common Terminology Criteria for Adverse Events, V 4.03. The number and percentage of subjects experiencing an AE/SAE will be stratified by system organ class, or a preferred term, and severity of the adverse event, and recorded and tabulated overall by each sub-strata. For more details, refer to Section 9.

Key Words: Ichthyosis, secukinumab, IL-17, biologic, monoclonal antibody

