Index. CISI is a validated score that assesses individual scores for erythema, scaling and alopecia, but is limited in that it is not a single score, includes a feature found in the minority of patients (alopecia) and includes non-uniform Likert scales (0-4+ or 0-5+). M-CISI eliminates the alopecia score, adopts a 5-point Likert for erythema and scaling, and averages the erythema and scaling scores for a single global assessment; it is a new scale that is being validated herein but will not be used for endpoints. IASI is a composite score based on the global CISI score that captures differences in severity in different body regions as a function of their body surface area and also standardizes the number of choices within the Likert scales for erythema and scaling. As in the EASI score for AD and the PASI score for psoriasis, IASI evaluates erythema and scaling as 0-4+ in severity at each of 4 locations: head and neck (including scalp); arms (including palms); legs (including soles); and trunk, prorated based on body surface area in these sites and the percentage of involvement in each of these sites (total possible score for each is 24 and total composite score is 48). To include a patient-reported severity score, we will use the Congenital Ichthyosis Severity Index, which has been validated for patient use (Kamalpour et al 2010), and the m-CISI. We will also pilot in the US a complex, non-validated burden of disease scoring system proposed by Bodemer et al in France, which heavily weighs associated morbidity (contractures, ectropion, mouth tightness, fissures) in addition to other measures of severity. All investigators/ sub-investigators will be trained based on photographs before study initiation to uniformly assign CISI, m-CISI, Bodemer, and IASI scores. A huge issue is the paucity of validated scores for ichthyosis severity. Our evaluations will be performed concurrently (but without conferring) by two investigators to allow inter-rater reliability, as well as at screening and again at baseline (at 3-4 weeks to minimize recall bias) for assessing test-retest reliability. As such, we hope to use this opportunity to assess reliability in these un-validated instruments. Patient-reported itch will be quantified on a 0-10 numerical rating scale (NRS) and by 5-D itch score (Elman et al 2009); a 1-10 score pain assessment is part of the Bodemer scale. The Yale Severity Index was recently developed and tested at a recent meeting of the Foundation for Ichthyosis and Related Skin Types. It includes a 0-4+ scale for erythema and for scaling, and provides pictorial representations for comparison, dividing scaling into lamellar and keratoderma scale scores. This study is the first time it will be applied to patients in an investigation.

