9.6. Analysis of Reliability

To determine inter-rater reliability, the two trained blinded investigators at each medical center will perform all assessments. To study intra-rater (test-retest) reliability, measures will be carried out by the subject (for the patient-reported severity outcome) and by the same two physicians (for the disease scores) at both screening and baseline visits, which will be separated by 3-4 weeks to minimize recall bias. Intra-rater and inter-rater reliability will be assessed by the intraclass correlation (ICC) for agreement (Shrout and Fleiss, 1979) and will be calculated within the linear mixed-effects model framework (Eldridge et al, 2009). The ICC for the inter-rater agreement will be calculated in the random coefficient model with covariates center and random intercepts for the patient and the physician. Bland-Altman plots will also be used to study patterns of agreements. As per Cicchetti (Cicchetti et al, 1994), interpretation for kappa or ICC for inter-rater agreement measures will be as follows: poor <0.40; fair 0.40-0.59; good 0.60-0.74; excellent 0.75-1.00.

10. ETHICAL CONSIDERATIONS.

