Appendix 5: Bodemer Scale

Product: Secukinumab
 Protocol Number: CAIN457AUS05T
 Date: 14 July 2018

(a) BODY SURFACE AREA WITH SCALES **(b) BODY SURFACE AREA WITH ERYTHEMA**

EXTENT: A =%

EXTENT: B =%

(c) PRURITUS: (C) (Value in cm)

PRURITUS (0 – 10) 0 _____ 10
 VISUAL ANALOGUE SCALE (average for the last 3 last days and nights)

(d) SKIN PAIN: (D) (Value in cm)

SKIN PAIN (0 – 10) 0 _____ 10
 VISUAL ANALOGUE SCALE (average for the last 3 last days and nights)

(e) SEVERITY OF 10 SYMPTOMS: (E) (Cumulated severity score for 10 symptoms: total value ranging from 0 to 60)

SCORE = A/10 + B/10 + C + D + E = / 100

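### The inter-rater ICC for the Bodemer score is planned on a total in which 20 of 100 points are itch and pain marks, most plausibly the patient's own; physician agreement should be judged on the other 80 points

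*Combined protocol and SAP*

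**What the plan says.** The Synopsis note under Efficacy Assessments has the severity scores "performed in tandem but blindly and without conferring by two physicians (IASI, CISI, m-CISI, Bodemer, Yale" so that inter-rater reliability can be assessed. It adds the subject as a further rater for CISI and m-CISI only.

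Section 9.6 states that "the two trained blinded investigators at each medical center will perform all assessments". It takes the inter-rater ICC from a model with random intercepts for patient and physician and a centre covariate, and adds Bland-Altman plots. The cut-offs are: poor below 0.40, fair from 0.40, good from 0.60, excellent from 0.75. No Bodemer item is excluded and no physician-only subscore is defined.

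Appendix 5 gives the only Bodemer score: "SCORE = A/10 + B/10 + C + D + E = / 100". A and B are percentages of body surface with scale and with erythema. C and D, pruritus and skin pain, are each marked from 0 to 10 on a "VISUAL ANALOGUE SCALE (average for the last 3 last days and nights". E is a "Cumulated severity score for 10 symptoms: total value ranging from 0 to 60".

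Section 2.1 treats itch and pain as patient-reported and makes a 50% fall in the Bodemer score a secondary endpoint. Section 2.3 lists inter-rater reliability as exploratory. Section 6.1.9 calls the Bodemer system non-validated and says that "a 1-10 score pain assessment is part of the Bodemer scale".

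**The concern.** An inter-rater ICC divides the variance between patients by that variance plus rater and residual error. A value common to both raters' totals enlarges the between-patient part and adds nothing to the error. Itch and pain over the preceding three days and nights cannot be seen at a visit, so C and D are best read as the patient's answers. The ICC of the total would then credit the physicians with agreement on items that they do not rate.

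Checking the reliability of scales not yet validated is a stated aim (2.3, 6.1.9). The Bodemer category will naturally be read beside those for IASI and the Yale index, which contain no itch or pain items. A category raised by patient marks would make that comparison uneven.

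**Working it through.** **1. Scale maximum (Appendix 5).** 100/10 + 100/10 + 10 + 10 + 10 × 6 = 100, as stated. C + D contribute 20; A/10 + B/10 + E contribute 10 + 10 + 60 = 80.

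**2. Formula.** Let the physician part have between-patient variance S and rater-plus-residual variance e. Let M = C + D be common to both physicians, with variance V and covariance K with the patient-level physician part.

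- ICC of the physician part = S/(S + e)
- ICC of the total = (S + V + 2K)/(S + V + 2K + e)

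The second is larger whenever V + 2K > 0. With v = SD(M)/√S and correlation rho, this means rho > −v/2.

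**3. Size under independence (K = 0).** Then ICC(total) = s + (1 − s) × ICC(physician part), where s = V/(V + S + e). The documents give no SDs, so these are assumptions: SD 2.5 per mark, correlation 0.5 between marks, SD 8-12 for the observed physician part.

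- V = 2 × 6.25 + 2 × 0.5 × 6.25 = 18.75
- SD 12: s = 18.75/(18.75 + 144) = 0.115
- SD 8: s = 18.75/(18.75 + 64) = 0.227

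| Physician-part ICC | Total, SD 12 | Total, SD 8 | Category |
|---|---|---|---|
| 0.35 | 0.425 | 0.497 | poor becomes fair |
| 0.45 | 0.513 | 0.575 | fair, unchanged |
| 0.50 | 0.558 | 0.613 | fair, or good at the upper end |
| 0.65 | 0.690 | 0.729 | good, unchanged |
| 0.80 | 0.823 | 0.845 | excellent, unchanged |

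For 0.50 to reach 0.60, 0.50 + 0.50s ≥ 0.60, so s ≥ 0.20. The physician-part variance must then be at most 4 × 18.75 = 75, an SD of 8.66 or less.

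**4. Effect of correlation.** At a physician-part ICC of 0.50, set S = e = 1. The assumptions in step 3 correspond to v = √(18.75/72) = 0.51 (SD 12) and √(18.75/32) = 0.77 (SD 8). On a separate assumed grid:

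- v = 0.25 to 0.6 with rho = 0 to 0.5: the total reads 0.515 to 0.662.
- v = 0.4, rho = 0.3: (1 + 0.16 + 0.24)/(1.40 + 1) = 0.583.
- v = 0.25, rho = −0.3: (1 + 0.0625 − 0.15)/(0.9125 + 1) = 0.477, a fall.

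A simulation of 4,000 samples of 40 patients and two raters (v = 0.4, rho = 0.3, physician-part ICC 0.50) gave mean ICCs of 0.487 for the physician part and 0.570 for the total. In 24% of samples the total reached 0.60 while the physician part did not.

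**5. Separate marks for each physician.** If the patient marks twice with an assumed same-visit repeatability of 0.95, each mark sum adds error variance v² × 0.05/0.95. With rho = 0.3, an ICC of 0.50 reads 0.547 (v = 0.25) to 0.628 (v = 0.6), against 0.548 to 0.632 with shared marks.

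**6. Bland-Altman.** With shared marks, (P1 + M) − (P2 + M) = P1 − P2, where P1 and P2 are the two physicians' parts. The mean difference and limits of agreement are the same for the total and the 80-point part.

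**The case against.** A reader might infer that the plan gives both physicians the same patient marks and so produces a biased ICC. The documents do not support that in full.

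- **Who marks C and D is not stated.** Appendix 5 does not say, nor whether one mark serves both forms. Section 6.1.9 ties patient-reported itch to the numerical rating scale and the 5-D score, and Appendix 10 has its own itch and pain scales. Section 2.1 therefore does not settle the matter for the Bodemer marks. Two physicians working without conferring might each obtain a mark. This stands as a limit on certainty. Step 5 shows that separate marks make little difference if they are highly repeatable, but that repeatability is itself assumed.
- **The ICC of the total is not a wrong number.** The secondary endpoint uses the 0-100 score, and the ICC of that score properly answers how far it depends on which physician completes it. This stands. Physician agreement on what physicians rate is a different question, and the cut-offs will be read as answering it.
- **A change of category is not established.** At 0.50 the shift reaches good only in a small corner of the assumed range, and 0.45, 0.65 and 0.80 change nothing. This stands, although 0.35 changes category throughout.
- **The planned Bland-Altman limits already show physician disagreement undiluted if the marks are shared.** This stands; the gap is in the ICC and its label.

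**Conclusion.** The point holds in a limited form. Section 9.6 would grade the Bodemer score on a total in which 20 of 100 points are most plausibly patient marks. With shared or nearly shared marks, that ICC exceeds the ICC of the physician-rated items unless rho falls below about −v/2, which is possible but unlikely for a burden-of-disease score.

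The size cannot be fixed from the documents. Under the assumptions in step 3, 0.50 reads about 0.56-0.61. The matter is confined to the exploratory reliability objective: the primary IASI analysis and the treatment comparisons do not use this ICC. It is a worthwhile refinement, and it does not make the planned ICC of the total invalid.

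**What to change.** In section 9.6, add that for the Bodemer score the inter-rater ICC will be computed on A/10 + B/10 + E (0-80), with the category cut-offs applied to that result when physician agreement is judged. The ICC of the 0-100 total will also be reported, labelled as the reliability of the score as used and as including patient-marked items.

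In Appendix 5, state that C and D are recorded once per visit from the subject. At the same time, reconcile the pain range, which starts at 1 in section 6.1.9 and at 0 in Appendix 5. The Bland-Altman limits need no change.

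The cost is a sentence in 9.6 and a line on the form. Appendix 5 already has A to E as separate entries, so no new data are needed. The downside is that the reported physician ICC may be less favourable.
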